
 
 										
 
 -		
 
											-										Page 1 of 3
-																					

Study Treatment : Alpha-1 MP			
I. Event Information			
1. Report Status  Initial  Follow-up	2. Date of this Report: ___/___/____ <small>DD MMM YYYY</small>	3. Country of Origin 	4. BDSS# (Company use) _____
5. Date of Birth ___/___/____ <small>DD MMM YYYY</small>	6. Gender  Male  Female	7. Weight  lb  kg	
8. Race  White or Caucasian  Black or African American  Asian  American Indian or Alaskan Native  Native Hawaiian or Other Pacific Islander  Other, specify: _____		9. Reason for Seriousness (check all that apply):  Resulted in death, if yes please complete section 18.  Life-threatening  Required/prolonged hospitalization on ___/___/____ <small>DD MMM YYYY</small>  Persistent or significant disability/incapacity  Congenital anomaly/birth defect  Important medical event: _____	
10. Ethnicity  Hispanic or Latino  Not Hispanic or Latino			
11. Event Term/Diagnosis 			
12. Describe details of event (attach additional sheet, if extra space is needed) 			
13. Event Onset/Start Date ___/___/____ <small>DD MMM YYYY</small> Start Time: ___:___ (24 hrs)	14. Event Stop Date  Ongoing ___/___/____ <small>DD MMM YYYY</small> Stop Time: ___:___ (24 hrs)	15. Relationship to Study Treatment  Unrelated/Not related, specify event cause _____  Doubtful/ Unlikely Related (classified as potentially related)  Possibly Related  Probably Related  Definitely Related	

Subject No.	Serious Adverse Event Report																								

 
 												
 
 -		
 
													-												Page 2 of 3
-																									

16. Severity  Mild  Moderate  Severe	17. Event Outcome  Recovered/Resolved  Recovering/Resolving  Recovered/Resolved with Sequelae  Not Recovered/Not Resolved  Fatal (see block #18)  Unknown	18. Death Details Date of death: ___/___/___ DD MMM YYYY Autopsy  Yes  No Specify why not : _____ Is death certificate attached?  Yes  No
--	--	---

II. Study Treatment Information

19. Study Treatment started on ___/___/___ DD MMM YYYY :___ (24 hrs)	20. Study Treatment stopped on ___/___/___ DD MMM YYYY :___ (24 hrs)	21. Frequency of dosing	22. Route of administration/Mode of Topical application (check all that apply)
23. Lot number	24. Expiration Date	25. Dose	26. Action taken with study treatment due to this SAE (check all that apply)  No change/None  Dose reduced  Restarted  Interrupted  Discontinued  Other, specify: _____
27. Did event abate after stopping or reducing study treatment?  Yes  No  Not Applicable		28. Did event reappear after reintroduction of study treatment?  Yes  No  Not Applicable	

III. Other Medical Information

29. Medical History	30. Relevant Lab/Confirmatory tests: include units and reference ranges/imaging reports (OR attach the report)  Check if reports are attached
----------------------------	---

31. Treatment Medications: Drug(s) used to treat serious adverse event.

Trade and Generic name	Total daily dose	Route of administration	Start Date [dd/mm/yyyy]	Stop Date [dd/mm/yyyy]	Indication

Subject No.	Serious Adverse Event Report																				

 
  	 	 	 	 	 	 	 	 	 	
 
 -		
 
											-										Page 3 of 3
-																					

31a. Other non-drug treatments for the SAE (e.g. surgery, etc.)

32. Concomitant drug(s): Only those drugs and other therapies the subject received at onset of the event (including other therapies) or up to 1 month prior to the event; exclude those to treat event.

Trade and Generic name	Total daily dose	Route of administration	Start Date [dd/mm/yyyy]	Stop Date [dd/mm/yyyy]	Indication

IV. Reporter/Investigator Information

33. Reporter's name/Title (please print)	34. Reporter's Phone #	35. Reporter's e-mail
36. Principal Investigator Name (please print)	37. Principal Investigator's Phone #	
38. Principal Investigator's Signature	39. Date	
40. Hospital Name and Address		

Please submit Hospital Discharge Summary for hospital admissions
 Please submit relevant test results and lab tests to provide support
 Submit additional sheets, if extra space is needed.

Please send Serious Adverse Event report by e-mail to:

Eastern Japan Pharmacovigilance Division, CMIC Co., Ltd. within 24 hours of notification.
 E-mail: [REDACTED]
 FAX (back-up only): [REDACTED]

A3.2 Supplemental Event Form

GRIFOLS

Study Number: GT11401

Subject No.	Serious Adverse Event Report
 - 	Page 1 of 1

Directions: Enter additional serious adverse events including supplemental event data. Choose the correct answer and enter the corresponding number in the block provided. For "Relationship", if #1 "Not Related" is chosen, ensure to specify the cause.

Event/Diagnosis	Event Start Date (dd/mm/yyyy)	Event Stop Date (dd/mm/yyyy)	Relationship to Study Drug	Action Taken with Study Drug	Severity	Outcome	Did event abate after stopping or reducing drug? (Yes/No)	Did event reappear after reintroduction of drug? (Yes/No)
			1. Unrelated/Not related-specify 2. Doubtful/Unlikely (classified as related) 3. Possibly Related 4. Probably Related 5. Definitely Related	1. No change 2. Dose reduced 3. Interrupted 4. Discontinued 5. Other, Specify	1. Mild 2. Moderate 3. Severe	1. Recovered/Resolved 2. Recovering/Resolving 3. Recovered/Resolved with Sequelae 4. Not Recovered/Not Resolved 5. Fatal (see block #18 on main SAE form) 6. Unknown		

Version 1.0: 01October 2015

A3.3 Pregnancy Report Form

GRIFOLS

Study Number: GTI1401

Subject No. 

	Pregnancy Report Form Page 1 of 2
--	---

PART A Initial Follow-up

Study Treatment: Alpha-1 MP			
I. Patient Identification			
1. Date of this Report: DD / MMM / YYYY	2. Initials PRIVATE	3. Gender  Male  Female	4. BDSS# (Company use)
5. Date of Birth DD / MMM / YYYY	6. Height  in  cm	7. Race  White or Caucasian  Black or African American  American Indian or Alaskan Native  Native Hawaiian/Other Pacific Islander  Asian  Other, specify: _____	
8. Age at Onset (years)	9. Weight  lb  kg	12. Study Withdrawal:  No  Yes, Date DD / MMM / YYYY  Unknown	
10. Ethnicity  Hispanic or Latino  Not Hispanic or Latino		11. Fetal Drug Exposure  via Mother  via Father	
II. Maternal Identification <small>(**Complete only if Fetal Exposure is via Father**)</small>			
13. Initials PRIVATE	14. Date of Birth DD / MMM / YYYY	15. Ethnicity  Hispanic or Latino  Not Hispanic or Latino	16. Race NOTE: Add Ethnicity here  White or Caucasian  Black or African American  American Indian or Alaskan Native  Native Hawaiian/Other Pacific Islander  Asian  Other, specify: _____
17. Age at Onset (years)	18. Weight  lb  kg	19. Height  in  cm	
III. Further Details of Pregnancy			
20. Date of Last Menstrual Period  Unknown DD / MMM / YYYY	21. Expected Date of Conception DD / MMM / YYYY	22. Expected Date of Delivery DD / MMM / YYYY	23. Gestational age at exposure to study treatment:  N/A Wks: _____ Days: _____
24. Date of Positive Pregnancy Test DD / MMM / YYYY	26. Previous Pregnancies: Total #: _____ FullTerm: _____ Premature: _____ Spontaneous Abortions: _____	27. Maternal Health Status  Diabetes  Hypertension during or prior to pregnancy  Other, specify: _____	
25. Was serum b-HCG performed?  No  Yes, Date: DD / MMM / YYYY	28. Social Habits During this Pregnancy  Smoking, # of cigarettes per day: _____  Alcohol consumption, # of drinks per week: _____  Drug use, details (confidential): _____		
IV. Study Treatment Information			
29. Study Treatment Start Date DD / MMM / YYYY	30. Study Treatment Stop Date DD / MMM / YYYY	31. Dose (specify units)	32. Route of administration
		33. Lot number:	34. Expiration Date:
V. Other Concomitant Medication Information			
35. Trade / Generic Name	Total Daily Dose	Route of administration	Start Date [dd/mmm/yyyy]
			Stop Date [dd/mmm/yyyy]
			Indication
VI. Reporter/Investigator Information			
36. Reporter's name/Title (please print)		37. Reporters Phone #	38. Reporters e-mail
39. Investigator Name (please print)		40. Investigator's Phone #	
41. Investigator's Signature		42. Date	

Please send Pregnancy Report Form by e-mail to Eastern Japan Pharmacovigilance Division, CMIC Co., Ltd.
 within 24 hours of notification.
 E-mail: [REDACTED]
 FAX (back-up only): [REDACTED]

Subject No. 

	Pregnancy Report Form Page 2 of 2
--	---

Part B Initial Follow-up

I. Maternal Outcome					
1. Were there any maternal complications during the pregnancy or delivery?  No  Yes, specify:					 No information available, specify reason:
2. Date of abortion: (dd/mm/yy)  N/A _____ / _____ / _____ DD/ MM/ YY  Spontaneous abortion  Elective abortion  Therapeutic abortion, reason for therapeutic abortion:					
II. Fetal Outcome					
 No information available  Live birth  Still birth  Multiple birth					
4. Date of Delivery _____ / _____ / _____ DD/ MM/ YY	5. Gestational age at delivery _____	6. Type of Delivery	7. Gender  Male  Female		
8. Birth length  in  cm	9. Birth Weight  lb  kg	10. Apgar Score – 1 Min	11. Apgar Score – 5 Mins	12. Apgar Score – 10 Min	

Alpha ₁ -PI	Alpha ₁ -proteinase inhibitor
ALT	Alanine aminotransferase
AST	Aspartate transaminase
ATS	American Thoracic Society
AUC	Area under the concentration-time curve
BLQ	Below limit of quantification
C _{max}	Maximum concentration
COPD	Chronic obstructive pulmonary disease
CRF	Case report form
CV	Coefficient of variation
FEV ₁	Forced expiratory volume in 1 second
FVC	Forced vital capacity
GCP	Good Clinical Practice
HAV	Hepatitis A virus
HBV	Hepatitis B virus
HCV	Hepatitis C virus
HIV	Human immunodeficiency virus
IgA	Immunoglobulin A
IgG	Immunoglobulin G
IgM	Immunoglobulin M
MedDRA [®]	Medical Dictionary for Regulatory Activities
NE	Neutrophil elastase
PFT	Pulmonary Function Test
PI*MM	Proteinase inhibitor homozygote for normal M allele
PI*(null)(null)	Proteinase inhibitor homozygote for (null) allele
PI*SZ	Proteinase inhibitor heterozygote for S and Z deficiency alleles

PI*Z	Proteinase inhibitor Z deficiency allele
PI*ZZ	Proteinase inhibitor homozygote for Z deficiency allele
pH	Potential of hydrogen; acidity/alkalinity measure
PK	Pharmacokinetics
SAE	Serious adverse event
SAP	Statistical analysis plan
SD	Standard deviation
$t_{1/2}$	Terminal half-life
TEAE	Treatment-emergent adverse event
t_{max}	Time to reach Cmax
US	United States
WHO-DD	World health organization drug dictionary

1 Purpose of the Analysis

The purpose of this statistical analysis plan (SAP) is to outline the planned analyses to support the completion of the clinical study report (CSR) for protocol GTI1401 and GTI1401-OLE. The planned analyses identified in this SAP will be included in regulatory submissions and/or future manuscripts. Exploratory analyses not identified or defined in this SAP may be performed to support the clinical development program. Any post hoc or unplanned analyses performed and not identified in this SAP will be documented in the respective CSR.

2 Introduction

Alpha₁-antitrypsin deficiency (AATD) is a genetic disorder in which mutations of the SERPINA1 gene (a member of the SERPIN, serine protease inhibitor gene family) lead to a reduced serum level of the serine protease inhibitor called alpha₁-proteinase inhibitor (alpha₁-PI) or, historically, alpha₁-antitrypsin. AATD manifests clinically as pulmonary emphysema, chronic obstructive pulmonary disease (COPD), and liver cirrhosis.

The most frequent mutation causing severe AATD is called PI*Z and was first described in a Swedish patient with emphysema. PI*MM (normal) individuals have serum alpha₁-PI levels in the range of 20 to 53 µM; however, PI*ZZ (homozygous abnormal) individuals with AATD have serum alpha₁-PI levels in the range of 2 to 10.2 µM. The estimated world-wide prevalence of PI*ZZ and PI*SZ (heterozygous abnormal) individuals is approximately 163,700 and 903,000, respectively.

Like other hereditary disorders, AATD is relatively rare (e.g., has orphan drug designation); however, it is extremely rare among Asians. In 2000, a survey supported by the Japanese Ministry of Health and Welfare identified only 16 individuals in Japan with documented AATD. AATD in Japanese patients exhibits unique features compared to AATD in Caucasians, including the lack of a PI*Z variant and a high incidence of the S_{iiyama} deficiency AATD variant. In Japanese patients homozygous for the S_{iiyama} variant, serum alpha₁-PI levels are in the range of 2.1 to 7.7 µM. Japanese normal individuals have serum alpha₁-PI levels in the range of 21 to 34 µM (94 to 150 mg/dL as measured by nephelometry, which is used as the laboratory test standard values).

Augmentation therapy with intravenous (IV) alpha₁-PI is administered in patients with AATD to increase the low serum concentrations in this patient population. This usage is intended to bolster the protective protease inhibitory shield against increased numbers of lung neutrophils releasing increased concentrations of NE, leading to a corrected protease: antiprotease imbalance. The restored antiprotease shield then protects the lung from elastolytic damage and slows the development of pulmonary emphysema.

Alpha₁-PI (human), Prolastin[®], was licensed for use as augmentation therapy for AATD, at a dose of 60 mg/kg weekly, in the United States (US) in 1987 and in Germany in 1988. To date, Prolastin[®] has been approved in 20 countries including the United States and

European countries. Subsequently, Grifols incorporated modifications into the Prolastin manufacturing process to produce alpha₁-PI (human), modified process (Alpha-1 MP). This modified process results in an increased yield of alpha₁-PI and a product with twice the alpha₁-PI concentration with an improved pathogen safety profile and higher purity compared to Prolastin. Alpha-1 MP is approved for 60 mg/kg weekly IV administration in the US, Canada, Argentina, Columbia, Turkey, Chile and Australia for the treatment of patients with severe AATD and clinically evident emphysema under the trade name Prolastin[®]-C.

Japanese patients with AATD exhibit very different genotypes of AATD compared to the rest of the world, and the number of Japanese patients with AATD is extremely small. These subjects can exhibit symptoms of emphysema-typed COPD and therefore, will have clinically evident emphysema and along with alpha₁-PI deficiency. The safety and PK of augmentation therapy with Alpha-1 MP to increase serum alpha₁-PI levels has not been evaluated in Japanese patients with AATD. Thus, Grifols Therapeutics Inc. and Grifols Japan K.K. is conducting a study to assess the safety and PK of 60 mg/kg Alpha-1 MP administered by weekly IV infusions over 8 weeks in Japanese subjects with AATD.

3 Objectives

3.1 Primary Objectives

The primary objective of GTI1401 study is to evaluate the safety of 60 mg/kg Alpha-1 MP administered by weekly IV infusions over eight weeks in Japanese subjects with AATD.

The primary objective of GTI1401-OLE study is to evaluate the long-term safety of 60 mg/kg Alpha-1 MP administered by weekly IV infusions for approximately one year or longer (can be renewed annually with the consent of the subjects) in adult subjects with AATD in Japan.

3.2 Secondary Objectives

The secondary objective of GTI1401 study is to evaluate the trough level of total alpha₁-PI for weekly IV infusions of 60 mg/kg Alpha-1 MP in Japanese subjects with AATD.

The secondary objective of GTI1401-OLE study is not set up.

3.3 Exploratory Objectives

The exploratory objective of GTI1401 is to measure the following PK parameters for Alpha₁-PI at steady state at the end of the 8-week treatment period.

- $AUC_{0-7 \text{ days}}$
Area under the concentration-time curve (AUC) from Day 0 to Day 7, calculated at steady state at the end of the 8-week treatment period.
- C_{\max}
Maximum concentration
- t_{\max}
The observed time to reach C_{\max}
- $t_{1/2}$
Terminal half-life

The exploratory objective of GTI1401-OLE is to perform CT scan (densitometry) at Ext Week 52. The CT scan data will be accumulated for the future evaluation of lung density.

- CT scan (densitometry)
Note: Subjects will undergo CT scanning for diagnosis of clinically apparent pulmonary emphysema in GTI1401 study. This CT scan data will also serve as the baseline measurement of lung density for GTI1401-OLE study.

4 Investigational Plan

4.1 Study Design and Plan

GTI1401 study is a multi-center, open-label, trial to evaluate the safety and PK of weekly IV infusions of 60 mg/kg Alpha-1 MP in Japanese subjects with AATD. At least three adult subjects will be enrolled in the study. The study consists of an up to three-week Screening Period, and an eight-week open-label Treatment Period including a one-week PK Assessment Period after the last infusion. At the Week 9 visit when the PK evaluation period is completed, subjects will be asked whether they would like to participate in an extension trial (GTI1401-OLE). For subjects not intending to participate in the extension trial, the date of follow-up/study completion visit (30 days [4 weeks] after the last dose of the investigational drug) will be arranged. The total duration of study participation for subjects who complete the study will be up to 14 weeks.

After providing informed consent at the Screening Visit, subjects will be evaluated for study eligibility during the Screening Period (up to three weeks); for study inclusion and exclusion criteria. Eligible subjects will enter the eight-week Treatment Period to receive a total of eight weekly IV infusions of 60 mg/kg Alpha-1 MP; subjects will receive their first infusion of Alpha-1 MP at the Week 1 (Baseline) Visit. During the Treatment Period, weekly infusions of Alpha-1 MP will be performed at the study site during scheduled study visits at Weeks 1 (Baseline), 2, 3, 4, 5, 6, 7, and 8. Subjects will receive their last infusion of Alpha-1 MP at the Week 8 Visit and will then enter the one-week

PK Assessment Period. During the PK Assessment Period, subjects have a last PK blood sampling study visit at Week 9. A Follow-Up/Final Visit (30 days [4 weeks] post last study drug infusion) will occur for subjects who will not participate in Study GTI1401-OLE.

[figure not shown]
All subjects will have a blood sample collected at Weeks 1 (Baseline), 7, and 8 (prior to the infusion of Alpha-1 MP) and Week 9 which will be used for the measurement of trough alpha₁-PI levels.

Blood samples for PK parameters will be collected beginning at Week 8 and the collection of blood samples will extend into Week 9. The pre-infusion serial PK sample at Week 8 and the last serial PK sample (7 days after the Week 8 infusion) at Week 9 will also serve as trough blood samples for Weeks 8 and 9. The specific timing of all 10 serial blood samples includes:

- Immediately prior to infusion
- Immediately after infusion completion (after sodium chloride [NaCl] flush) (0 hour)
- 15 minutes after infusion completion
- 2 hours after infusion completion
- 4 hours after infusion completion
- 8 hours after infusion completion
- 24±4 hours (1 day after infusion completion)
- 48±4 hours (2 days after infusion completion)
- 120 hours ± 1 day (5 days after infusion completion)
- 168 hours ± 1 day (7 days after infusion completion) (Week 9 Visit)

At the Week 9 visit, subjects have the option to participate in an open-label extension (OLE) study (GTI1401-OLE) in which subjects, if they opt to enroll, will continue to receive 60 mg/kg Alpha-1 MP for at least another year (with the optional subsequent annual extensions) to assess the long-term safety of Alpha-1 MP. Week 9 of the GTI1401 study is also the first week of the extension study (GTI1401-OLE). If subjects do not opt to participate in Study GTI140-OLE, they will come back to the clinic 30 days (4 weeks) after the last Alpha-1 MP infusion for the Follow-Up/End of Study Visit (Week 12).

A schematic of the overall study design is shown in Figure 1 below. The schedule of events for GTI1401 and GTI1401-OLE studies can be found in appendix 1 and appendix 2.

^a Final Visit/Early Termination = Follow-up/Final Evaluation Visit. Subjects who discontinue early from the study will need to complete this study visit 30days (4 weeks) after the last study drug infusion.

^b At the Week 9 Visit, subjects will be given the option to participate in the GTI1401-OLE. If they are enrolled in Study GTI1401-OLE, the Week 9 visit will be their End of Study Visit of GTI1401 study.

Figure 1 Overall Study Schema

4.2 Study Variables

No efficacy variables will be assessed for the studies. The variables to be assessed for GTI1401 and GTI1401-OLE studies are as follows:

- Adverse events, ADRs, serious AEs (SAEs), and discontinuations due to AEs or SAEs
- Vital signs (heart rate, blood pressure, respiratory rate, and temperature)
- COPD exacerbations
- Pulmonary function tests :
 - Forced Expiratory Volume in 1 second (FEV₁)
 - Forced Vital Capacity (FVC)
- Clinical laboratory parameters:
 - Chemistry
 - Hematology
 - Urinalysis
- Alpha₁-PI trough level
- PK parameters (GTI1401 study only):
 - AUC_{0-7 days}
 - C_{max}
 - t_{max}

- $t_{1/2}$
- CT scan (densitometry)

5 General Statistical Considerations

All analyses will be conducted using SAS Version 9.3 or higher.

Pharmacokinetic evaluations, descriptive statistical analysis of concentrations and PK parameters according to non-compartmental standard methods, as well as graphical representation of concentrations will be performed using the computer program Pharsight Phoenix WinNonlin (Version 6.1 or higher).

Unless otherwise specified, the results from GTI1401 and GTI1401-OLE will be presented separately.

Unless otherwise noted, for continuous variables, descriptive statistics will include the number of non-missing values, mean, standard deviation, median, minimum and maximum. For categorical variables, descriptive statistics will include counts and percentages per category.

5.1 PK Data Handling

For PK parameter estimation, the actual sample time instead of nominal time will be used. For the last time point (168 hours post infusion), if the actual time deviates from the scheduled time, the interpolation or extrapolation will be used to obtain the $AUC_{0-7\text{days}}$.

When BLQ values are recorded, adopt the half value of the readable numeric value (2.5 mg/dL) for summarizing data.

5.2 Handling of Missing values

Missing values will not be imputed unless otherwise specified.

For Adverse Event

Any missing severity/relationship will be accounted as “worst case” as related in the tables.

5.3 Safety Data Handling

5.3.1 Definition of Baseline

Baseline evaluations will be those collected (non-missing) closest to and prior to the first study drug infusion, which will be conducted –within 21 days of Week 1. For both GTI1401 and GTI1401-OLE, the baseline is the baseline visit at Week 1 in GTI1401 study.

For Pulmonary Function Tests

Values collected at “PRE-BRONCHODILATOR” time-point in screening visit will be defined as baseline for “PRE-BRONCHODILATOR”. Also values collected at “POST-BRONCHODILATOR” time-point in screening visit will be defined as baseline for “POST-BRONCHODILATOR”.

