Week 1 (Baseline)	
[Before intravenous infusion of Alpha-1 MP]
 
 
• Reevaluation of the inclusion/exclusion criteria 
• Body weight: Recorded body weight will be used to calculate the Alpha-1 MP dose administered at the Week 1 (baseline) visit. This recorded body weight will be used for dose calculation until the next scheduled body weight measurement. 
• Laboratory tests (refer to Section 4.7.3) 
Urine samples: Urinalysis
 
Blood samples:
 
Viral safety assessment: Blood samples for viral nucleic acid amplification (NAT) and viral serologic test will be collected at the Week 1 (baseline) visit. However, the collected samples will be tested only if the subject shows clinical signs or symptoms

	
suggestive of viral infection during the trial period. All collected blood samples will be stored until completion of the tests in this clinical trial (GTI1401) and the extension trial (GTI1401-OLE).
 
Blood chemistry, hematology, alpha₁-PI concentrations
 
 • COPD exacerbation (refer to Section 4.6.1) • Adverse events • Concomitant medications • Vital signs (pulse rate, blood pressure, respiratory rate, and body temperature) immediately before the start of intravenous infusion of Alpha-1 MP 
[At the time of intravenous infusion (intravenous drip) of Alpha-1 MP]
 
 • Intravenous infusion of Alpha-1 MP • Vital signs (pulse rate, blood pressure, respiratory rate, and body temperature) immediately after the completion of intravenous infusion of Alpha-1 MP • 12-lead ECG immediately after the end of intravenous infusion of Alpha-1 MP • Observation of the subject for at least 30 minutes after the intravenous infusion

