	
 • Laboratory tests (refer to Section 4.7.3) 
 Urine samples: Urinalysis 
 Urine pregnancy test: To be performed only in women of childbearing potential Urinary cotinine level Blood samples: Alpha₁-PI trough concentrations (To be used as a PK sample at 168 hours after completion of the intravenous infusion [7 days after completion of the intravenous infusion at the Week 8 visit]) 
 Blood chemistry, hematology • PFT (FEV₁ and FVC) before and after administration of a bronchodilator (refer to Section 4.6.2) • COPD exacerbation (refer to Section 4.6.1) • Adverse events • Concomitant medications • Vital signs (pulse rate, blood pressure, respiratory rate, and body temperature) • 12-lead ECG (Note: For subjects to be enrolled in the GTI1401-OLE, this 12-lead ECG will be performed prior to the Alpha-1 MP infusion for GTI1401-OLE).
--	---

4.7.2.3 Visit for follow-up/study completion (Week 12) (for subjects not entering the extension trial [GTI1401-OLE])

Subjects not entering the extension trial (GTI1401-OLE) will visit the study center at 30 days (4 weeks) after completion of the last intravenous infusion of the investigational drug (Week 8) and at 3 weeks after the Week 9 visit to complete the follow-up/study completion examinations (Week 12). The date of Week 12 visit will be scheduled in the week specified in the protocol according to the actual date of the Week 1 (baseline) visit (± 1 day).

Visit	Trial Procedures and Evaluations
Visit for follow-up/study completion (Week 12) (for subjects not entering the extension trial [GT11401-OLE])	
 • Physical examination (excluding breast and urogenital examination) • Laboratory tests (refer to Section 4.7.3) 
 Urine samples: Urinalysis Urine pregnancy test: To be performed only in women of childbearing potential. Urinary cotinine level Blood samples: Blood chemistry, hematology • PFT (FEV₁ and FVC) before and after administration of a bronchodilator (refer to Section 4.6.2) • COPD exacerbation (refer to Section 4.6.1) • Adverse events • Concomitant medications • Vital signs (pulse rate, blood pressure, respiratory rate, and body temperature)

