5.3.2 Visit Windows for Safety Analyses

The date of all visits after the screening visit and the Week 1 (baseline) visit will be arranged within a time window of ± 1 day.

If an observation is missing at a specific scheduled visit, the value at that visit will be set to missing.

Visit recorded on CRF will be used as Analysis visit except Baseline visit.

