11.4 Electrocardiogram

11.4.1 Summary Table of Electrocardiogram		
Population	:	Safety population
Contents	:	Shift tables for electrocardiogram will be provided. The analysis variables are displayed in Table D. For electrocardiogram results, a data listing will be provided.
Analysis Visit for 1401	:	Baseline, Week 9
Analysis Visit for 1401-OLE	:	Baseline, Ext Week 26, Ext Week 52

Table D:

Contents	Category
Electrocardiogram	Normal Abnormal

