11.4 Electrocardiogram
11.4.1 Summary Table of Electrocardiogram

Safety population

		N=88			
Electrocardiogram		Normal	Abnormal	Missing	Total
Week 9	Normal	xx	xx	xx	xx
	Abnormal	xx	xx	xx	xx
	Missing	xx	xx	xx	xx
	Total	xx	xx	xx	xx

> Analysis visit for 1401-OLE;
Baseline
Ext Week 26
Ext Week 52

GTI 1401
11 Safety Analysis

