11.4 Electrocardiogram
11.4.2 Listing of Electrocardiogram

Safety population

Subject Number	Visit	Baseline	Date of Electrocardiogram Performed	Value
xxxx	Week 1	Y	yyyy-mm-dd	NORMAL
	Week 9		yyyy-mm-dd	NORMAL
xxxx	Week 1	Y	yyyy-mm-dd	ABNORMAL
	Week 9		yyyy-mm-dd	ABNORMAL
...

>Sort order;
Subject Number, Visit

GTI 1401
11 Safety Analysis

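### SAP 5.3.1 gives two different ECG baselines, one of them recorded after the first infusion, and neither lets the planned shift table fully show an ECG change that begins at that infusion

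*SAP*

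**What the plan says.** **Baseline rule.** SAP 5.3.1 opens with "Baseline evaluations will be those collected (non-missing) closest to and prior to the first study drug infusion", with a window reaching back 21 days from Week 1. The next sentence reads "For both GTI1401 and GTI1401-OLE, the baseline is the baseline visit at Week 1 in GTI1401 study". A separate rule follows for pulmonary function tests, whose baseline is Screening. ECG has no such rule. SAP 5.3.2 adds "Visit recorded on CRF will be used as Analysis visit except Baseline visit", so the CRF visit label does not settle what counts as baseline; 5.3.1 has to.

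**ECG schedule.** Protocol 4.7.2.1 lists an ECG at Screening. In Protocol 4.7.2.2 the pre-infusion block for Week 1 contains no ECG; the infusion block has "12-lead ECG immediately after the end of intravenous infusion of Alpha-1 MP". The third ECG is at Week 9, and for subjects going into the extension "this 12-lead ECG will be performed prior to the Alpha-1 MP infusion for GTI1401-OLE". Protocol Appendix 1 and SAP Appendix 1 mark the same three visits.

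**ECG analysis.** SAP 11.4.1 plans a Normal/Abnormal shift table whose GTI1401 visits are "Baseline, Week 9". The shell in the Layout Plan has rows for Week 9 only. The shell for Listing 11.4.2 shows "Week 1 Y yyyy-mm-dd NORMAL", where the Y is the baseline flag, and it has no Screening row. For the extension, SAP 11.4.1 plans shifts at Ext Weeks 26 and 52, but the extension schedule in SAP Appendix 2 contains no ECG.

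**The concern.** A baseline for a safety shift table should be untreated. For laboratory tests and vital signs the two sentences of 5.3.1 agree, because both are measured before the infusion at Week 1. Cotinine and pulmonary function are not measured at Week 1, so Screening is their only possible baseline. ECG is the one tabulated measure whose sole Week 1 value is post-infusion, so the two sentences give conflicting instructions.

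Safety is the primary objective, and this is the only planned ECG summary. If the Week 1 tracing is the reference, an abnormality that starts with the first infusion and persists looks pre-existing, and one that resolves looks like an improvement on treatment. If Screening is the reference, the only ECG taken straight after an infusion is in no summary table. With a minimum target of 3 subjects, one misclassified subject could be a third of the table (1/3).

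**Working it through.** The plan gives no figure to reproduce. The check is which ECG each rule selects, followed by a complete enumeration of outcomes.

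**Step 1: which ECG is baseline?**

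| ECG | Timing | Last value before first infusion (5.3.1, sentence 1) | Week 1 visit (5.3.1, sentence 2) |
|---|---|---|---|
| Screening | before first infusion | selected | not selected |
| Week 1 | after end of first infusion | not eligible | selected |
| Week 9 | about 7 days after the Week 8 infusion | not eligible | not selected |

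**Step 2: how does each pattern tabulate?** Each of the three ECGs is Normal (N) or Abnormal (A), giving 2 × 2 × 2 = 8 patterns, written in the order Screening, Week 1 post-infusion, Week 9. The planned cell is baseline > Week 9.

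| Pattern | Week 1 baseline | Screening baseline | Same cell? |
|---|---|---|---|
| N N N | N>N | N>N | yes |
| N N A | N>A | N>A | yes |
| N A N | A>N | N>N | no |
| N A A | A>A | N>A | no |
| A N N | N>N | A>N | no |
| A N A | N>A | A>A | no |
| A A N | A>N | A>N | yes |
| A A A | A>A | A>A | yes |

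Four of the 8 patterns change cell with the choice of rule: NAN, NAA, ANN and ANA.

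**Step 3: is onset at the first infusion visible?** The relevant patterns are those with Screening N and Week 1 A, namely NAN and NAA. The number shown as N>A is:

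- Week 1 baseline, Week 9 row: 0 of 2. NAN reads as improvement and NAA as pre-existing.
- Screening baseline, Week 9 row only: 1 of 2. NAA is shown, but in the same cell as NNA, so its timing is lost. NAN is missed.
- Screening baseline, with Week 1 post-infusion and Week 9 rows: 2 of 2, both in the Week 1 row.

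The Week 1 baseline also produces one false new abnormality: ANA, already abnormal at Screening, is shown as N>A.

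These are counts of logical patterns, not probabilities. The documents give no rates with which to weight them.

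**The case against.** The strongest reply is that 5.3.1 need not contradict itself. Its first sentence can be taken as the operative rule, and its 21-day window includes Screening. The second sentence names both studies, so it may mean only that the extension reuses the GTI1401 baseline and does not start a new one. The SAP 5.3.2 exemption of baseline from CRF visit labels fits a derived pre-dose value. The cotinine listing, which flags Screening without any stated exception, shows that the second sentence is not always applied literally. Mock shells also contain illustrative or carried-over rows: the vital signs shell has a Week 9 post-infusion row although GTI1401 has no infusion at Week 9.

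That reading is plausible, but it does not clear the problem. Cotinine has no Week 1 value, so its flag could only fall on Screening and says little about ECG. For ECG, where both values exist, the shell flags Week 1 and leaves no place for the Screening result. A programmer working from it would use the post-dose tracing as the reference.

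It is also fair that nothing in the documents requires an acute post-infusion ECG to be tabulated. A Screening-to-Week 9 table is coherent on its own terms, ECG is not among the listed study variables (Protocol 4.6, SAP 4.2), and with a handful of subjects a reader can scan the listing. This limits the impact. It helps less than it seems to, because the listing as drawn labels the post-dose ECG as baseline and omits Screening, although Protocol 8.1.2 says all subject data will be listed.

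The extension-study mismatch is a separate matter. The extension protocol is not available here, so it supports a query and no more.

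**Conclusion.** The concern holds. As written, SAP 5.3.1 supports two ECG baselines, one of them post-dose, and the ECG listing shell has adopted the post-dose one. The choice changes the shift cell for 4 of 8 patterns. A new abnormality arising at the first infusion is shown in 0 of 2 patterns with the Week 1 baseline and in 1 of 2 with Screening, against 2 of 2 if Screening is the baseline and Week 1 is a post-baseline row.

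This rests on the ECG schedule as the protocol gives it, with no unscheduled pre-infusion ECG at Week 1, and on the shells being programmed as drawn. It should be fixed, but its reach is modest: one descriptive table, individual ECG results in a listing, and clinically relevant findings reportable as adverse events.

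**What to change.** - **SAP 5.3.1:** add an ECG exception beside the one for pulmonary function tests, stating that the Screening ECG is the baseline.
- **SAP 11.4.1 and its shell:** set the GTI1401 visits to Baseline (Screening), Week 1 (immediately after infusion) and Week 9, with Week 1 as a post-baseline row.
- **Listing 11.4.2:** add a Screening row, move the baseline flag to it, and label the Week 1 row as post-infusion.
- **Extension study:** use the same Screening baseline for any ECG table, and reconcile the Ext Week 26 and 52 ECG visits in SAP 11.4.1 with SAP Appendix 2, which lists no ECG.

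For GTI1401 the cost is SAP and shell wording only, since all three ECGs are already scheduled. The extension item needs a check against that study's schedule.
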